**Site Responsible PI:** **Phone:** **Institution(s):**

**3. DRUG / DEVICE INFORMATION N/A:**

**Drug(s), Biologic(s):**  **Device(s) Name:** iThermonitor  
**Provided by:** **Provided by:** Raiing Medical Company  
**IND Exempt:**  -or- **IDE Exempt:**  -or-  
**IND#:** **Holder Type:** [pull down] **IDE #:** **Holder Type:** [pull down]  
**IND Holder Name:** **IDE Holder Name:**

**4. PROTOCOL COORDINATION, FUNDING, MODE**

**Regulatory Sponsor:** **Funding/Support** (check all that apply):  
DF/HCC Investigator  Industry: Raiing Medical Company  
 Federal Organization:  
**CTEP Study:** No Grant #:  
 Internal Funding:  
 Non-Federal:  
 Other:

**Protocol Involves** (check all that apply as listed in the protocol document, even if not part of the research but is mandated by the protocol document):

- |   |  |   |
|---|--|---|
|  Chemotherapy                           |  Hormone Therapy           |  Medical Record Review             |
|  Immunotherapy                          |  Vaccine                   |  Questionnaires/Surveys/Interviews |
|  Surgery                                |  Data Repository           |  Radiological Exams                           |
|  Bone Marrow/Stem Cell Transplant       |  Exercise/Physical Therapy |  Required Biopsy Study                        |
|  Cell Based Therapy                     |  Genetic Studies           |  Human Embryonic Stem Cell                    |
|  Gene Transfer (use of recombinant DNA) |  Human Material Banking    |  Quality of Life                              |
|  Radiation Therapy                      |  Human Material Collection |  Other: use of study device        |

**5. SUBJECT POPULATION (also applies to medical record review and specimen collection studies)**

**Total Study-Wide Enrollment Goal:** 25 dyads **Greater than 25% of the overall study accrual will be at DF/HCC:**  Yes  No  
**Total DF/HCC Estimated Enrollment Goal:** 25 dyads **Adult Age Range:** 18+ **Pediatric Age Range:** 2-17  
**Will all subjects be recruited from pediatric clinics?**  Yes  No  
**If enrolling both adults and pediatric subjects, anticipated percent of pediatric subjects:** 50% (1/2 of each dyads)  
**Retrospective Medical Record Reviews only (Please provide date range):** from to

**8. DF/HCC INITIATED STUDIES ONLY - INSTITUTIONAL PARTICIPANTS UNDER OTHER IRB (N/A: )**

**DF/HCC Multi-Center Protocols:** (list institution/location) **DF/PCC Network Affiliates:** (list institution/location)

Recruitment	

• Solicit participation of pediatric oncology team at the MGH Cancer Centers

• Potential subjects identified from the MGH Cancer Centers

Enrollment	

• Study staff meets with subject/caregiver for consent

• Enrollment procedures, baseline data collection and initial set-up

During the study	

• Subjects continue care as usual

• Use the iThermonitor

Close-out	

• Complete final questionnaires and other closeout procedures

Use Feasibility of the iThermonitor in Pediatric Patients on Myelosuppressive Therapies for  
Acute Leukemia and other Childhood Cancers

[name]., M.P.H.

Detailed IRB protocol

6.1 Partners Broadcast Ad

## 1.0 Introduction

### 1.1 Overview

This is a pilot study to evaluate the use feasibility of the iThermonitor, a continuous temperature monitoring device, as a clinical support and patient self-management tool in the management of pediatric patients on myelosuppressive therapies for acute leukemia and other childhood cancers.

### 1.2 Background and Rationale

Since 1975, the incidence rate of childhood cancers has been steadily increasing by an average of 0.6% every year. Based on 2014 data, it is estimated that 1 in 285 children will be diagnosed with cancer before age 20 years. Cancer is also expected to be the cause of death in about 1,960 children in 2014 making it the second leading cause of death in children. This rise in cancer rates corresponds with increased rates of four childhood cancers: acute lymphocytic leukemia, acute myeloid leukemia, non-Hodgkin lymphoma, and testicular germ cell tumors.

Specifically, acute lymphocytic leukemia is the most common childhood cancer, accounting for 26% and 80% of all cancers and leukemia respectively in children aged 0-14 years. Due to improvement in treatment strategies, the 5-year survival rate has increased from 57% in 1975 to about 90% in 2009. In general, the treatment of ALL is in three phases over 2-3 years: remission induction, consolidation and maintenance. Patients who relapse may be eligible for stem cell transplantation. Patients undergoing treatment for acute leukemia are particularly prone to profound neutropenia due to intensive chemotherapy during the induction phase. This neutropenic state is expected to last about 10 days during intensive phase of treatment. Similarly, patients undergoing allogeneic stem cell transplantation and other myelosuppressive therapies are also at high risk for neutropenia.

Neutropenia predisposes patients to significant risk for infectious complications which increases morbidity and mortality. Usually, fever is the first clinical sign of the inflammatory response to the infective process; and early detection is an indication for empiric antimicrobial therapy and further evaluation to determine risk for sepsis. Today, broad-spectrum antimicrobial therapy at the first detection of fever has helped significantly decrease the mortality associated with neutropenia in the intensive phase of chemotherapy. Therefore, early detection of fever, through regular temperature monitoring, in a neutropenic patient is critical to improved clinical outcome. Vigilance on the part of care providers and caregivers is crucial to early detection. Traditionally, this is simply done through episodic oral or axillary monitoring of temperature. In this study, we propose to test the use feasibility of an innovative device that continuously monitors body temperature as a clinical decision support tool in pediatric patients undergoing myelosuppressive therapies for acute leukemias and other childhood cancers.

The iThermonitor, a FDA class II device, is a high accuracy device that continuously captures body temperature and automatically delivers the data wirelessly (via blue tooth or wi-

fi) to mobile devices or for cloud storage. It has the capacity to store 10 days worth of recorded temperature data. The device can be used to effortlessly monitor patients on a continuous basis during the intensive phase of chemotherapy as opposed to the usual episodic oral or axillary measurements. It is also able to generate and deliver out-of-range temperature alerts on a mobile application for care givers or providers. It also provides care providers an opportunity to remotely monitor their patients' temperature in the immediate period after discharge from the hospital. Therefore, we hypothesize that the iThermonitor can serve as a feasible clinical decision support in the management of pediatric patients undergoing intensive treatments for acute leukemia and other childhood cancers. The device hasn't been previously tested for use in pediatric patients and finding from this study could generate useful data for future studies.

### **Proposed Study**

This study will be implemented as a pilot study to test the use feasibility of the iThermonitor as a clinical decision support for continuous temperature monitoring in a dyad of 25 pediatrics patients, (aged 2yrs – 17yrs) on myelosuppressive therapies for acute leukemia and other childhood cancers at the MGH Pediatric Hematology and Oncology group and their caregivers. The iThermonitor will be used by patients and their caregivers for 14 days of data collection. There will be up to be two study visits: study enrollment and study closeout. Participants will be given the option to complete study closeout online via RedCap. REDCap is a secure, web-based application for building and managing on line surveys. The REDCap version offers a more convenient means for survey administration and eliminates the need for an in-person closeout visit. Should the participant choose this option, a member of the study staff will email a link to the RedCap survey via RedCap's secure email system.

We have chosen to implement this study as a feasibility study because our goal is to determine if continuous temperature monitoring by the iThermonitor can work in home settings. This is in keeping with the definition for feasibility studies proposed by the National Institute for Health Research Evaluation, Trials and Studies Coordinating Centre (NETSCC), which states that "feasibility studies are pieces of research done before a main study in order to answer the question 'can it work?'" Bowen et al further suggests that they could be used to answer the questions – "does it work and will it work?" and that they are used to determine whether an intervention is appropriate for further testing. Based on the paper by Bowen et al describing the diverse types of feasibility studies funded by the National Cancer Institute, this study meets the criteria for conducting feasibility studies. According to them, one of the indications for a feasibility study is when "there are few previously published studies or existing data using a specific intervention technique". To our knowledge, we are not aware of any previous research exploring continuous temperature monitoring in pediatric oncology patients on myelosuppressive therapies. Therefore, findings from this study have the potential to advance knowledge about the management of fever in pediatric patients on myelosuppressive therapies.

## **2.0 Objectives**

### **2.1 Hypothesis**

We hypothesize that at least 80% of study subjects will be able to successfully use the iThermonitor to continuously monitor their body temperature. A subject must be able to view temperature data on the provided iPad mini at least 80% of the time in the study to be considered successful. "Time in the study" here is defined as the number of days the subject spends in the study which is expected to be 14 days.

## 2.2 Primary and Secondary aims:

2.21 The primary aim of this trial is to assess the use feasibility of the iThermonitor as a clinical decision support tool in the management of patients on myelosuppressive therapies for acute leukemia and other childhood cancers. We will consider the iThermonitor as a feasible clinical decision support tool if it successfully captures body temperature data, transmit and displays the data on the iPad mini in at least 80% of the study subjects. We will also assess the ability of the device to alert the caregiver if the temperature falls outside of pre-set range which is defined for all patients as temperature less than or equal to 96 and greater than or equal to 100.

## 2.22 Secondary outcomes:

- Usability, acceptability and satisfaction with the iThermonitor.
- Caregiver engagement with the iThermonitor.
- Effect of the study on caregiver anxiety.

## 3.0 Research Subject Selection

Pediatric patients undergoing myelosuppressive therapies for acute leukemias and other childhood cancers at the Massachusetts General Hospital Cancer Center and their caregivers will be eligible to participate in this study. Eligible patients and their caregivers will be enrolled to participate in this study as a dyad.

### 3.1 Inclusion/Exclusion

All male and female patients, regardless of ethnicity, are candidates for enrollment in this study if they meet all of the inclusion and exclusion criteria listed below.

#### 3.1a Inclusion criteria - Child:

- Pediatrics patients aged 2-17 years undergoing myelosuppressive therapies for acute leukemias and other childhood cancers.
- If applicable, willingness of the patient to shave axillary (armpit) hair.
- Ability of patient (if old enough) to read and speak English
- Has a caregiver,  $\geq 18$  years of age that is willing to participate in the study

### 3.1b Inclusion criteria – Caregiver/Parent:

- Caregivers (parents or legal guardians) must give informed consent
- Ability of caregiver to read and speak English

### 3.1b Justification of inclusion criteria:

- The iThermonitor is recommended for use only in children aged 2 years and above.
- Shaving is recommended for older children who have attained puberty because the device works best when in contact with flat and smooth skin.
- Participation of caregivers is needed because they will be required to monitor temperature data on the provided iPad mini and also to help answer questions pertaining to the usability of the iThermonitor.
- Fluency in English is required because the study materials will be administered only in English.
- No study procedure will be performed without informed consent from the parents or legal guardians of patients.

### 3.1c Exclusion criteria

- Patients with history of allergy to hydrogel dressing or ongoing skin diseases.
- Patients with ongoing febrile illness or documented infectious disease.

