### 3.1d Justification for exclusion criteria

- We are excluding patients with history of allergy to hydrogel dressing or skin diseases to limit the possibilities of adverse skin reactions.
- We are excluding patients with ongoing febrile illness or documented infectious disease to decrease the chances of study-related adverse effects.

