### 6.1 Primary and secondary endpoints

6.1a Primary outcome measurement: use feasibility of the iThermonitor will be assessed by ability of the device to successfully capture, transmit and display the patient's body temperature data on the study iPad mini. To limit recall bias, subjects will be required to log (Appendix 5) the ability to view the temperature data on the iPad mini once a day for the entire duration of the study. The device will be deemed a feasible continuous temperature monitoring tool if at least 80% of study subjects are able to successfully use the iThermonitor to monitor their body temperature. A subject must be able to view temperature data on the provided iPad mini at least 80% of the time in the study to be considered successful. "Time in the study" here is defined as the number of days the subject spends in the study which is expected to be two weeks.

6.1b Secondary outcomes: secondary outcomes which will be assessed at the end of the study include:

- i. Usability, acceptability and satisfaction with the iThermonitor. This will be assessed by questionnaires specifically designed for this study. We will be assessing ease of use, acceptability, connection and use problems like the device falling off the skin, usefulness of out-of-range temperature alerts and adverse reactions. We will also assess to see if the device helps to build caregiver self-efficacy skills in caring for the patient.
- ii. Caregiver engagement with the iThermonitor. This will be assessed by time to first measurement and upload from the time of discharge and also by the frequency of logins to the iThermonitor app.
- iii. Caregiver anxiety will be assessed using the GAD-7 questionnaire.

6.2 Sample size and statistical power or precision associated with the sample size: The length of time required to accrue an adequate number of subjects to the study should be indicated.

We will be able to estimate a feasibility success rate of 80% to within a 95% confidence interval of +/- 16% with a sample size of 25 evaluable patients. This is in keeping with a

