## Section 9 Biocompatibility

### 1. Patient--Contact Material Identification

The patient--contact components and materials are presented as follows:

Table 9--1 Patient Contact Material Identification

Components	Material	Contact Level	Contact Duration
Double coated medical tape	Medical Tape	Surface	Short-term (<24h)
Shell	ABS	Surface	Short-term (<24h)

*NOTE: The contact level and contact duration are determined according to Annex A of ISO 10993--1:2009 Biological evaluation of medical devices — Part 1 Evaluation and testing within a risk management process.*

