**Proposed Features and Benefits:**

- Hypoallergenic Silicone Pressure Sensitive Adhesive
- Flexible, Conformable
- Excellent Initial Skin Adhesion
- No Natural Rubber Latex
- EtO Sterilization Compatible Only
- Premium Clear Polypropylene Liner

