## Using and maintaining the iThermonitor

- Charge the iPad regularly and keep the iThermonitor app open. Do not log out of the app.
- Make sure the Bluetooth is in the on position.
  - If you have a Wi-Fi connection in your home, connect the iPad to the Wi-Fi to allow the iThermonitor to sync for data collection.
- DO NOT change settings of the iPad or the iThermonitor app.
- DO NOT get the iThermonitor wet (shower, bath swimming, etc).
- DO NOT wear the iThermonitor at one side for more than 24 consecutive hours. Change sides everyday to wear it for continuous monitoring.
- If your child feels unwell (uncomfortable or allergic) when using the patch, replace it with another type of adhesive dressing based on your doctor's advice. A fully-covered patch larger than 76mm×62mm should be used.
- Do not reuse the patches. If a patch is already folded over, a new patch is required.

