**13. What problems did you experience?**  
(Please circle **all that apply**)

- a. Problems keeping the device on my child's body
- b. Problems linking the device with my smartphones
- c. Problems with the iThermonitor battery
- d. Problems setting out-of-range temperature alerts
- e. Other problems: \_\_\_\_\_

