#### III. Inclusion/Exclusion Criteria

Inclusion Criteria (From IRB approved protocol)	Yes	No	Supporting Documentation*
1. Dyad consists of a pediatric patient aged 2-17 years undergoing myelosuppressive therapies for acute leukemia and other childhood cancers.			
2. Dyad also includes a caregiver, $\geq 18$ years of age that is willing to participate in the study.			
3. Ability of caregiver and or patient (if old enough) to read and speak English.			
4. If applicable, willingness of the patient to shave axillary (armpit) hair.			
5. Caregiver (parent or legal guardian) must give informed consent for dyad participation.			
Exclusion Criteria (From IRB approved protocol)			
1. Patient has a history of allergy to hydrogel dressing or ongoing skin diseases			
2. Patients with ongoing febrile illness or documented infectious disease.			

\*All subject files must include supporting documentation to confirm subject eligibility. The method of confirmation can include, but is not limited to, laboratory test results, radiology test results, subject self-report, and medical record review.

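### The allergy exclusion names only hydrogel although the device papers list tape and a silicone adhesive, and the close-out survey has no skin-reaction item

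*Combined protocol and SAP*

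**What the plan says.** **Screening.** Section 3.1c excludes "Patients with history of allergy to hydrogel dressing or ongoing skin diseases". Exclusion 1 of the eligibility checklist (Appendix 5.1) reads "Patient has a history of allergy to hydrogel dressing or ongoing skin diseases". Section 3.1d gives the reason: "We are excluding patients with history of allergy to hydrogel dressing or skin diseases to limit the possibilities of adverse skin reactions". Hydrogel is the only allergen named in any of the three places.

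**Attachment as the protocol describes it.** Section 5.3, section 5.7 and the letter to oncologists (Appendix 2.1) all say that the device is held on by hydrogel. Section 5.7 adds that a skin reaction to the device's adhesive surface cannot be excluded.

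**Attachment as the device papers describe it.** Table 9-1 in the biocompatibility section (Appendix 1.2) gives two patient-contact components: "Double coated medical tape" and an ABS shell. The supplier letter filed with it concerns 3M nonwoven tapes 2476 and 2476P. The information sheet for 2476P describes a single coated tape and lists "Hypoallergenic Silicone Pressure Sensitive Adhesive" among its features. The user manual (Appendix 1.4) tells caregivers of a child who is uncomfortable or allergic with the patch to "replace it with another type of adhesive dressing", on the doctor's advice.

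**Measuring reactions.** Section 6.1b item i lists what the study questionnaires will cover, including "usefulness of out-of-range temperature alerts and adverse reactions". Question 13 of the close-out survey (Appendix 4.1) offers trouble keeping the device on, linking it, "Problems with the iThermonitor battery", setting alerts, and an open other category.

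**The concern.** An allergy exclusion protects participants only if it names what they will wear. Here the criterion names one material and the device papers name others. A research assistant working from the checklist would ask about hydrogel. A parent who knows of a reaction to medical tape could truthfully answer no, and the child would be registered.

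The participants are children on myelosuppressive therapy who are to wear the device for 14 days, so an avoidable skin reaction matters. The second gap adds to the first. If a reaction occurs, the instrument that section 6.1b assigns to adverse reactions has no question that would count it, so the report could not give a questionnaire-based rate with a clear denominator.

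**Working it through.** The plan states no figure on this point that could be reproduced. The check is a comparison of texts.

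**1. What touches the skin**

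| Source | Material described |
|---|---|
| Sections 5.3 and 5.7, Appendix 2.1 | Hydrogel dressing |
| Table 9-1, Appendix 1.2 | Double coated tape; ABS shell |
| Supplier sheet for 2476P, Appendix 1.2 | Single coated tape, silicone adhesive |
| User manual, Appendix 1.4 | The supplied patch, or another adhesive dressing on a doctor's advice |

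The sources do not agree. The protocol and Table 9-1 differ on hydrogel against tape. Within the device papers, the table and the supplier sheet differ on double against single coating. Silicone is not in Table 9-1; it comes only from the supplier sheet, which is marked preliminary.

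**2. Who passes the criterion as written**

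Take a child with a documented allergy to tape or another adhesive, no allergy to hydrogel, no ongoing skin disease, no febrile illness and no documented infection.

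- First limb of 3.1c, hydrogel allergy: not met.
- Second limb, ongoing skin disease: not met, because a past contact allergy is not a current skin disease.
- The remaining exclusion, febrile illness or infection: not met.

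The child is not excluded. The result matters only if a tape or other adhesive is worn, which step 1 leaves open. If the patch really is hydrogel, the criterion fits the patch supplied. It would still not cover a substitute dressing permitted by the manual.

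**3. Criterion against its purpose**

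Section 3.1d says the exclusion is there to limit skin reactions, and section 5.7 locates the hazard in the adhesive surface. The screening question does not ask about adhesives.

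**4. Where a skin reaction would be recorded**

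- Close-out survey, questions 1 to 18: none asks about the skin. Question 12 asks about problems using the device, and a caregiver who answers no skips question 13. Question 14 is free text about the problems just marked. Question 18 offers a conversation with staff.
- Daily log (Appendix 5.2): two columns, whether the device stayed on and whether data could be viewed.
- Sections 5.71 and 5.73: all adverse events are documented with timing, intensity, seriousness and causality, logged, and followed.

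A reaction that comes to the study team's notice is therefore recorded as an adverse event. The questionnaire outcome named in section 6.1b has no item of its own.

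**The case against.** The strongest reply is that the study patch is hydrogel, as the protocol says throughout, and that the tape papers are regulatory attachments from the device manufacturer and its supplier. Those papers disagree with each other, and Section 9 refers to a separate biocompatibility exhibit. Some appendix pages are not in the text available here, so the absence of hydrogel from the visible listings does not prove that it is absent from the device papers. This stands. It is why the conclusion is conditional and why reconciliation comes first.

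Hydrogel may also be a loose name for whatever patch is supplied. The documents do not say so, and if it is, the wording still needs correcting.

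Further mitigations are fair. The supplier calls the adhesive hypoallergenic, the manual makes a change of dressing depend on a doctor's advice, treating oncologists help to identify candidates, and an investigator confirms eligibility. These bear on how likely a reaction is. They do not change what the criterion covers.

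Two stronger readings should be resisted.

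- *That the gap threatens the primary endpoint.* A reader might suppose that two reacting children turn 21/25 = 84% into 19/25 = 76%, below the 80% bar. No allergy rate in the documents supports the two. The manual provides for changing the patch, which need not mean stopping. If the two were instead dropped under the complete-case approach of section 6.8, the rate would be 19/23 = 82.6%. Even at 19/25 the exact 95% upper limit is about 91%, so the not-feasible rule in section 6.7 (upper limit below 80%) would not be triggered.
- *That adverse reactions go uncollected.* Sections 5.71 and 5.73 and the survey's free text show otherwise.

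**Conclusion.** The point holds as a conflict between passages with a safety consequence that depends on how the conflict is resolved. The documents do not establish that children will wear a silicone or tape adhesive. They do establish that the allergy screen covers only hydrogel while the device papers name other contact materials, and that a child with a known allergy to one of those would pass.

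The survey gap does not depend on which material is used: section 6.1b gives the questionnaires an outcome that the close-out survey does not ask about.

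No size can be given, because the documents contain no rate of tape or adhesive allergy. The sample size and primary analysis are unaffected. This is worth correcting because the change is small and the participants are vulnerable.

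**What to change.** 1. Reconcile section 5.3, Table 9-1, the 2476P sheet and the user manual, and state in one place which materials touch the skin, including any substitute dressing the study permits.
2. Once that is settled, align the allergy wording of section 3.1c and checklist exclusion 1 with the materials actually supplied or permitted. If the patch proves to be hydrogel only and no substitute is allowed, the present wording can stay.
3. Add one yes/no skin-reaction question to the close-out survey, placed so that the skip after question 12 does not bypass it, and report it as a count over the caregivers who answered.

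The cost is an edit to one criterion and one checklist line, one more survey question, and possibly the exclusion of a few children.
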